Falls are a major concern for people living in countries all over the world. Tens of millions of people who fall are seriously injured and hundreds of thousands of people who fall die every year. People who are dizzy are far more likely to fall. The researchers are particularly interested in working with people whose dizziness is caused by looking at checkerboard patterns, walking through grocery store aisles, riding in vehicles, or watching movies (visually-induced dizziness) since this problem affects adults who are healthy and adults who have a variety of health conditions. No diagnostic tests for this condition exist at this time and the treatments currently being used may result in worsening dizziness. This is a preliminary study of how human beings control balance and how symptoms of visually-induced dizziness may result in falls. The researchers created new tests of orientation and balance, as well as a new treatment for visually-induced dizziness. It is not known whether the new tests of orientation and balance are better, worse, or the same as existing tests in the ability to detect problems, nor is it known if the new treatment technique is any better, worse, or the same as existing treatments for dizziness and imbalance. However, the researchers believe that the new tests do improve the ability to detect problems. They also think that the treatment will result in less dizziness, better balance, and reduced risk of falling for those who receive it and that is it a better alternative to treatments that are already available to patients. In order to see if this is true, the researchers will use the new tests and treatments with healthy adults and adults who are affected by dizziness. All the people in this study will undergo the same tests and will receive the same treatment. Testing is done twice before and twice after the treatment period. The treatment is provided twice a week for three weeks in a row. The tests and treatments are done while standing on a computerized platform that measures balance and can tilt people from side to side. During these study procedures, participants wear virtual reality goggles that show them simple images in an otherwise dark environment. The goal of the tests and the treatment is for people to use what the feel to help them decide if the images shown inside the goggles are aligned with the person's sense of gravity. Participation in this study is voluntary and people who decide to participate may stop at any time without penalty. All people in this study will receive a modest payment as reimbursement for their time and effort.

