Gait Speed: A 10-meter walk test will be conducted with eyes open and eyes closed in accordance with previously published methodology(39). Participants will be allowed one practice trial for each condition.

Participation Timeline:

Including a telephone screening, there are 9 study contacts over 6 weeks. Questionnaires, as well as tests of verticality perception, balance, and gait are to be collected in weeks 1, 2, 4, and 5 (see Table 2, page 19). The intervention will be conducted 2 times during each twice-weekly visit in weeks 2, 3, and 4. This research is being conducted in the UW-Madison Neuromuscular Coordination Laboratory.

In order to substantially reduce the time each participant is required to be in the lab and increase accuracy of data collection, patient-reported outcomes will be administered via ICTR REDCap. Measures will be collected up to 24 hours before visits 1 and 2, as well as up to 24 hours after visit 3, and up to 24 hours before visit 4 in order to ensure patient-reported and performance-based outcomes are administered at the same time points. Pre-testing with the performance-based outcomes described in this protocol will occur at visit 1 and immediately prior to training during visit 2. Post-testing with the performance-based outcomes will take place immediately after training during visit 7, as well as during visit 8. The intervention will be provided during visits 2 and 3. The data collected at each time point is shown in Table 3.

Participants will be in "on treatment" status during weeks 2-4. "Off study" status coincides with the completion of post-testing.

	Week 0	Week 1	Week 2	Week 3	Week 4	Week 5
Activity						
Screening	Before enrolled					
Outcomes		Baseline 1	Baseline 2		Post-test 1	Post-test 2
Training			2x/week	2x/week	2x/week	

Table 2: Participation Timeline:

Table 3: Data Collected at Each Assessment Timepoint

Measure	Pre-test 1	Pre-test 2	Post-test 1	Post-test 2
VVAS	Х	Х	Х	Х
VRD-25	Х	Х	Х	Х
ABCS	Х	Х	Х	Х
DHI	Х	Х	Х	Х
VAPM	Х			Х
VRBQ	X			X
SVV	Х	Х	Х	Х

RFT	Х	Х	Х	Х
RDT	Х	Х	Х	Х
MBE	Х	Х	Х	Х
FGA	Х			Х
Gait Speed	Х			Х

Sample Size:

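### The Participation Timeline mixes two visit numberings: the last two questionnaire sets are tied to visits 3 and 4, but the performance post-tests they should accompany are at visits 7 and 8.

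*Combined protocol and SAP*

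**What the plan says.** Everything in conflict sits in one section, Participation Timeline.

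- Contacts: "Including a telephone screening, there are 9 study contacts over 6 weeks".
- Assessment weeks: "Questionnaires, as well as tests of verticality perception, balance, and gait are to be collected in weeks 1, 2, 4, and 5". Table 2 likewise places Post-test 1 in week 4 and Post-test 2 in week 5.
- Training: "The intervention will be conducted 2 times during each twice-weekly visit in weeks 2, 3, and 4".
- Questionnaire windows: in the 24 hours before visits 1 and 2, in the 24 hours after visit 3, and in the 24 hours before "visit 4 in order to ensure patient-reported and performance-based outcomes are administered at the same time points".
- Performance pre-tests: "Pre-testing with the performance-based outcomes described in this protocol will occur at visit 1 and immediately prior to training during visit 2".
- Performance post-tests: "Post-testing with the performance-based outcomes will take place immediately after training during visit 7, as well as during visit 8".
- Intervention visits: "The intervention will be provided during visits 2 and 3".

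Elsewhere, Trial Design gives six treatment sessions and two follow-up tests, and the lay summary says "Testing is done twice before and twice after the treatment period". Table 3 lists the instruments under Pre-test 1, Pre-test 2, Post-test 1 and Post-test 2, without weeks or visit numbers. Data Collection Methods says that REDCap sends the questionnaire emails automatically at the Table 3 timepoints.

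**The concern.** The questionnaire sentence states its own purpose, which is to coincide with the performance tests. It cannot do so if visits 3 and 4 belong to the same numbering as visits 7 and 8.

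Three planned analyses in Statistical Methods depend on this timing:

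- the pre-post comparison of the Visual Vertigo Analogue Scale, the only analysis named for reduced symptoms (Hypothesis B);
- the comparison of results at the end of training with those a week later, as far as it concerns questionnaires;
- the correlations between patient-reported and performance-based outcomes.

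If the post-test questionnaires were collected partway through training, the first would describe a partial course, the second would not describe retention, and the third would pair measures taken at different stages of treatment.

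**Working it through.** **Step 1. Reproduce the number of visits.** Three sources agree:

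- Contacts: 9 − 1 telephone screen = 8 visits.
- Table 2: 1 (week 1) + 3 weeks × 2 (weeks 2 to 4) + 1 (week 5) = 8 visits.
- Reimbursement (Recruitment and Retention Strategies): ($250 − $50 bonus) / $25 per visit = 8 visits.

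A schedule of four visits would give 4 + 1 = 5 contacts and 4 × $25 + $50 = $150. Neither matches the plan.

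**Step 2. Map the visits.** Assumption: visits are numbered in time order and the telephone screen is not numbered. The performance post-test sentence fits this.

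| Visit | Week | Content |
|---|---|---|
| 1 | 1 | Baseline 1 |
| 2 | 2 | Baseline 2, then session 1 |
| 3 | 2 | Session 2 |
| 4 | 3 | Session 3 |
| 5 | 3 | Session 4 |
| 6 | 4 | Session 5 |
| 7 | 4 | Session 6, then Post-test 1 |
| 8 | 5 | Post-test 2 |

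**Step 3. Read visits 3 and 4 on the eight-visit numbering.**

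- Third set, after visit 3: 2 of 6 sessions completed. At two rounds per session (Description of the Training Task), that is 4 of 12 rounds.
- Fourth set, before visit 4: still 2 of 6 sessions, so no session separates the two sets.
- Sessions still to come: 6 − 2 = 4 (visits 4 to 7).
- Distance from the matching performance post-test: 7 − 3 = 4 visits and 8 − 4 = 4 visits.

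**Step 4. Read visits 3 and 4 as the third and fourth assessment occasions.** They are then visits 7 and 8. Both sets follow 6 of 6 sessions and the distance is 0.

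**Step 5. Count what is exposed (Table 3).**

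- Four instruments (VVAS, VRD-25, ABCS, DHI) × 2 post-tests = 8 administrations.
- Two instruments (VAPM, VRBQ) × 1 post-test = 2 administrations.
- Total: 8 + 2 = 10 per participant, out of 4 × 4 + 2 × 2 = 20 over the whole study.

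Under Step 3 all 10 are mistimed; under Step 4, none.

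**Step 6. Sort the four sentences that carry visit numbers.** The post-test sentence (7, 8) needs the eight-visit numbering. The pre-test sentence (1, 2) fits either. The questionnaire sentence (1, 2, 3, 4) meets its own aim only on the assessment-occasion numbering. The intervention sentence (2, 3) also looks like assessment-occasion numbering, since the second and third assessments are the two that share a visit with training.

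**The case against.** The strongest reply is that the plan already resolves the matter. The weeks sentence, Table 2, the lay summary and the stated aim of the questionnaire sentence all place the last two sets at or after the end of training. The REDCap emails are tied to Table 3, whose Post-test 1 and Post-test 2 labels are the ones Table 2 puts in weeks 4 and 5. The literal eight-visit reading also requires setting the intervention sentence aside: if training were at visits 2 and 3, questionnaires after visit 3 and before visit 4 would both follow it. On this view the numbers 3 and 4 are an editorial slip.

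Most of this stands. The likely intent is weeks 4 and 5, and the harm arises only if the numbers are applied literally. What does not fall away is that the faulty sentence is the only text giving questionnaire visit numbers and 24-hour windows. Weeks alone do not supply them: week 4 contains both visit 6 and visit 7. Whoever turns Table 3 into dated invitations must either use the faulty sentence or overrule it, and nowhere does the plan define visits 3 and 4 as assessment occasions.

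A reader might go further and infer that the post-test questionnaires were, or will be, collected mid-treatment. The documents do not show which reading was used. A reader might also take the intervention sentence as a separate dispute over the number of sessions. It need not be: it is probably the same numbering slip, though it still has to be reconciled.

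**Conclusion.** The contradiction is certain; its consequence is conditional. Applied literally to the eight-visit schedule, 10 questionnaire administrations per participant would follow 2 of 6 sessions. If the weeks sentence and Table 2 are followed, none would. The figure counts administrations, not scores: the VRD-25 alone has two subscale scores and a total.

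Severity is minor to moderate. The patient-reported outcomes are listed as secondary or additional, and inferential analyses are described as hypothesis generating. It would be wrong to infer that the primary outcomes are compromised: the Rod and Disk Test, the other verticality tests and the balance test have their own, consistent visit numbers. No sample-size figure depends on this point. That the numbers 3 and 4 come from a four-assessment numbering is an inference, and so is the view that weeks 4 and 5 are intended.

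**What to change.** 1. In Participation Timeline, tie the third questionnaire window to the 24 hours after visit 7 and the fourth to the 24 hours before visit 8.
2. Add visit numbers 1, 2, 7 and 8 to the column heads of Table 3, so that the REDCap emails refer to one schedule.
3. Check the REDCap invitation settings against those visits.
4. If any questionnaires have already been collected, check their timestamps. The documents are mixed on this: Administrative Information describes recruitment as not yet open, while parts of Data Collection Methods, Harms and the consent section are in the past tense.
5. Reconcile the sentence placing the intervention at visits 2 and 3 with the six sessions in Trial Design and with Table 2.

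The cost is a wording amendment to one paragraph and one table head, a settings check and possibly a timestamp check. It adds no burden for participants.

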The intervention will result in reduced symptoms (Hypothesis B) and improved verticality perception (Hypothesis C). Also, changes in balance control will be detected by pre-post comparisons of the IP curves measured during visual-vestibular conflict (Hypothesis D).

Background and Rationale:

Falls result in significant morbidity for both younger and older adults and falls are the second leading cause of accidental or unintentional mortality worldwide (10). Fatal falls are most common in persons over 65 years old. Data from the United States shows that one out of five falls results in serious morbidities, such as a fracture or traumatic brain injury (11). A recent analysis of mortality data(12) reveals 29,666 Americans age 65 and older had a fatal fall in 2016. That same year, Wisconsin's fall-related death rate of 142.7 per 100,000 was the highest in the nation(12). Despite multidisciplinary efforts to address this public health crisis over the past two decades(13,14), the overall rate of fatal falls in older adults increased by 31% from 2007 to 2016(12). Thus, the need to improve knowledge about human balance control and falls prevention is more urgent than ever.

The issue of falls is a complex problem and many risk factors must be considered when designing falls prevention strategies. Strong associations exist between current and future falls and a history of falls, gait problems, walking aid use, vertigo, Parkinson's disease, and antiepileptic drug use(15). We are particularly interested in vertigo (dizziness) which is the third most common symptom reported in ambulatory settings(16) and has a strong association with falls as measured by a common test of sensory interaction in balance(17). We believe developing better methods of evaluating and treating patients with dizziness and imbalance is crucial to addressing this global public health crisis.

Our attention is focused on visually-induced dizziness because this condition is unique in that it cuts across populations, affecting persons with cognitive impairments, sensory system disturbances, and neurological conditions, as well as otherwise healthy adults and those who are experiencing physiological changes associated with ageing. Studying persons with visually-induced dizziness provides a model for advancing understanding the sensorimotor processes underlying human postural orientation and postural equilibrium, as well as the association between dizziness and falls.

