Trial Design: The study will be conducted in three phases. The first phase is for baseline testing. The second phase is when treatment occurs. The third phase is for follow up testing. Participants will be tested twice during the baseline and follow up phases. Six treatment sessions will occur during the treatment phase. Healthy adults (Group 1, n=15) and adults with self-reported visually-induced dizziness (Group 2, n=15) will undergo the same tests and will receive the same intervention.

METHODS: PARTICIPANTS, INTERVENTIONS, AND OUTCOMES

Study Setting:

This trial will be conducted at the University of Wisconsin-Madison, a level 1 research institution. Study visits will occur at the Neuromuscular Coordination Laboratory, [name], Director.

Eligibility:

Healthy Participants:

Inclusion Criteria: Participants must 1) be adults between the ages of 18 and 79 years old, 2) have normal self-reported cognitive function, 3) speak English fluently, 4) weigh less than 225 pounds and be less than 6'4", 5) be able to support their body weight in an upright posture for 15 minutes at a time, and 6) be able to follow the guidelines regarding permitted and prohibited additional treatments outlined in this protocol.

Exclusion Criteria: Participants must not 1) be pregnant or planning to become pregnant while in "on study" status, 2) have best-corrected visual acuity > 20/70, 3) have a self-reported, uncompensated, binocular vision abnormality, such as strabismus, amblyopia, or diplopia, 4) have peripheral neuropathy, and/or 5) have a self-reported history of frequent syncope (>1/month).

Participants with Visually-induced Dizziness:

Inclusion Criteria: Participants must 1) be adults between the ages of 18 and 79 years old, 2) have self-reported symptoms of visually-induced dizziness, 3) have normal self-reported cognitive function, 4) speak English fluently, 5) weigh less than 225 pounds and be less than 6'4", 6) be able to support their body weight in an upright posture for 15 minutes at a time, and 7) be able to follow the guidelines regarding permitted and prohibited additional treatments outlined in this protocol.

[figure not shown]

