Targeted emails will be sent to past participants who were enrolled in the study, "Reliability and Validity of a Next-generation Sensory Organization Test," IRB #2017-1081. Our prior IRB approval allowed for the retention of certain data to use for contacting those participants to invite them to participate in future research. We will send up to three recruitment emails inviting those subjects who self-identified as having visually-induced dizziness on the VVAS.

Targeted email campaigns will be sent to students, faculty, and staff associated with the UW-Madison Physical Therapy Program, Occupational Therapy Program, and Department of Kinesiology: The UW-Madison Department of Information Technology (DoIT) Mass Email service may be employed to recruit participants from the UW-Madison campus community. The educational experience of students in these programs may be enhanced by learning more about patient-reported and performance-based outcome measures utilized in this research. Faculty and staff may benefit by being exposed to research capabilities within the Departments of Kinesiology and Orthopedics and Rehabilitation as this could lead to generating ideas for future collaboration. Potential benefits regarding possible treatment effects are described elsewhere. [name] is an Associate Professor in the Department of Kinesiology and, therefore, may have a status relationship with individuals from the Department of Kinesiology. [name] was, therefore, be directly involved with recruiting and enrolling individuals associated with the Department of Kinesiology prior to enrollment closing. [name] involvement in recruitment and enrollment will be consistent with his COI management plan. [name] is a Professor in the Physical Therapy Program and will be blinded to whether or not any physical therapy students participate in this research. The mass email program provided by DoIT will be utilized to send these emails. The Health Sciences Institutional Review Board (HS-IRB) guidance for sending mass emails will be followed. One email will be sent per month until the required number of participants has been recruited.

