Direct recruitment and referrals may occur in UW Health Ear, Nose, and Throat clinics and other clinics where patients who may qualify for this research are routinely seen, the UW Health Middleton Physical Medicine and Rehabilitation clinics, the Neuro Outpatient Rehabilitation Clinic or the Yahara Clinic),

Justification of Direct Recruitment and Referrals: For persons who have already been identified in clinical care as having dizziness or balance disorders, participation in this research will not adversely affect their clinical care, rather it has the potential to enhance their care in the event any positive treatment effects occur. Clinic schedules will be reviewed by clinicians associated with the study team to determine if any patients may be potential participants. Recruiting participants without screening clinic schedules would increase the study costs related to advertisement and significantly prolong the recruitment period to twice or three-times as long.

METHODS: ASSIGNMENT OF INTERVENTIONS

Participant Screening:

[name] conducted a telephone screening of potential participants. Only those individuals who responded to a flier or recruitment email, or those who are identified within the context of clinical practice, as described in this protocol, will be contacted for screening. Up to 3 call to reach potential subjects by phone before discontinuing attempts to contact potential participants. No recruitment letters will be sent of those who cannot be reached by phone. The contact information for those who do not respond to voice messages will be shredded upon the completion of the study. The specific language used for the telephone screening is scripted.

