This trial follows a non-randomized, parallel groups design.

Blinding (masking):

It is not possible to mask participants from this behavioral intervention. Also, given the scope of the project and size of the study team, it is not practical to mask the researchers either.

METHODS: DATA COLLECTION, MANAGEMENT, AND ANALYSIS

Data Collection Methods:

Telephone Screening: During the telephone interview, [name] entered all demographic and screening data into these databases in data entry forms with fields that are programmed to only accept valid entries. These data will be verified with participants when they attend their first study visit.

Patient-reported Outcome Measures: Participants who consent to the use of email for study-related purposes will enter their own data for most patient-reported outcome measures via secure, direct links to the ICTR REDCap database that will be contained in emails that will be automatically sent by ICTR REDCap at the appropriate timepoints (Table 3). Data entry fields in ICTR OnCore and ICTR REDCap are programmed to only allow valid responses. Paper forms will be used at the appropriate time points for those subjects who do not consent to the use of email for study-related purposes.

Performance-based Outcome Measures: A data collection file will be created for each participant within the file structure of the KIINCE device, which is password protected and housed in a secure lab. Only the study team will have access to these files. The data file records the following information: participant ID, age, weight, overall height, height to deltoid process, height to axilla, height to greater trochanter, current date, current time, and all of the variables required to document performance during testing and training. These data will be uploaded to ICTR REDCap for further data management and analysis after the last participant completes the study. A copy of the data file will remain on the KIINCE device for up to 10 years. The study team will consult with [name], [contact], [contact] and [name], [contact], [contact] regarding storage of participant data on the KIINCE device and as needed for matters related to data storage and security.

Health Records:

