Study Management: The ICTR OnCore platform will be used for overall study management. In addition, ICTR REDCap will be used to collect patient-reported outcome measures through the use of surveys, as well as performance-based outcomes through the use of standardized forms. The ICTR REDCap and ICTR OnCore systems are password protected and user's roles are defined to allow appropriate access. [name] had completed training in ICTR OnCore for protocol, financial, and study coordinators, as well as the requisite training for ICTR REDCap. Fields are programmed to ensure the validity of the data.

Statistical Methods:

Data Analysis: Standard demographic data will be collected. Age, gender, height, weight, and body mass index will be summarized with descriptive statistics. Inferential analyses are expected to be hypotheses generating. Our a-priori alpha level for all analyses is 0.05.

All data collected will be entered in a custom-built project in the UW-Madison ICTR REDCap database so that it can be securely transferred to the study biostatistician (ICTR BERD). All analyses will be conducted using "R" for statistical computing version 3.5 or higher. The study biostatistician (ICTR BERD) will provide an independent review of the data analysis.

The specific aims for this trial and related analyses are as follows:

Aim 1 Analyses: The overall scores for each verticality perception test will be analyzed for sensitivity and specificity, positive and negative predicative values, likelihood ratio, and the area under the ROC curve (AUC) for correctly identifying self-reported visually-induced dizziness(44).

Aim 2 Analysis: Euclidian distance analyses(45) will be used to compare IP curves of healthy and symptomatic persons to determine if these curves have diagnostic value for visually-induced dizziness.

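### Aims 1 and 2 compare healthy and symptomatic adults aged 18 to 79 without balancing or adjusting for age or sex, so the AUC and IP-curve difference may partly reflect age

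*Combined protocol and SAP*

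**What the plan says.** **Groups.** Trial Design sets 15 healthy and 15 symptomatic participants. Under Allocation: "This trial follows a non-randomized, parallel groups design". Both inclusion lists in Eligibility require that participants "be adults between the ages of 18 and 79 years old". The two groups also share limits on weight, height and standing tolerance, self-reported normal cognition, and exclusions for poor acuity, uncompensated binocular vision problems, peripheral neuropathy and frequent syncope. No section sets an age band, quota, match or stratum for age or sex.

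**Recruitment.** Two routes are aimed at symptomatic people. One is emails to participants of an earlier study, "inviting those subjects who self-identified as having visually-induced dizziness on the VVAS". The other is clinic referral: "Direct recruitment and referrals may occur in UW Health Ear, Nose, and Throat clinics", among other clinics, justified for patients already known to have dizziness or balance disorders. The remaining routes are not tied to either group. They are posted advertisements, emails to clinical staff, and campus emails that "will be sent to students, faculty, and staff associated with the UW-Madison Physical Therapy Program" and related departments.

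**Analysis.** Data Analysis, under Statistical Methods, states: "Age, gender, height, weight, and body mass index will be summarized with descriptive statistics". Aim 1 then reports sensitivity, specificity, predictive values, likelihood ratio and AUC for identifying self-reported visually-induced dizziness. Aim 2 compares the IP curves of the two groups by Euclidean distance. Neither names a covariate. The same section calls the inferential analyses hypothesis generating.

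**The concern.** A variable confounds a two-group diagnostic comparison if it differs between the groups and also moves the test score. The protocol gives reason to think age could do both.

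- **Link to the condition.** The Recruitment background says motion sickness prevalence varies with age and gender, among other factors. Background and Rationale lists, among the people affected by visually-induced dizziness, "those who are experiencing physiological changes associated with ageing".
- **Link to what the tests measure.** Specific Aims includes older adults among those who experience disorientation and disequilibrium. The verticality battery and the IP curves are meant to capture these.

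The protocol already uses this reasoning once: pregnancy is excluded partly because its effect on postural control would confound the results. It does not apply the reasoning to age or sex within the admitted range.

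At stake is the interpretation of Aims 1 and 2. If the groups differ in age, some of the apparent accuracy, or of the IP-curve separation, could be an age effect credited to dizziness. If the gap runs the other way, a real difference could be hidden. With 15 per group, this is hard to separate afterwards if the ages overlap little.

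**Working it through.** **Inputs from the documents:** 15 per group (Trial Design); ages 18 to 79 in both groups (Eligibility); alpha 0.05 (Data Analysis).

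**Assumed, because the documents give neither:** within-group correlation r between score and age, 0 to 0.5; difference in mean age D, 0 to 1.5 within-group SDs. For scale, ages spread uniformly over 18 to 79 have SD (79 − 18)/√12 = 17.6 years. Scores are taken as normal with equal variance, and dizziness as having no true effect.

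**The plan's own figure.** Sample Size takes 15 per group from a published pilot-trial table. The usual two-arm formula, n = 2(1.960 + 1.282)²/d², gives 234, 85 and 43 per arm for d = 0.3, 0.5 and 0.7. Those sizes belong to the later main trial, so the mismatch is not an error, and 15 is taken as given.

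**Step 1: AUC from age alone.** The spurious standardized difference is r × D, and AUC = Φ(rD/√2).

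| r | D = 0 | D = 0.5 | D = 1.0 | D = 1.5 |
|---|---|---|---|---|
| 0 | 0.50 | 0.50 | 0.50 | 0.50 |
| 0.3 | 0.50 | 0.54 | 0.58 | 0.62 |
| 0.4 | 0.50 | 0.56 | 0.61 | 0.66 |
| 0.5 | 0.50 | 0.57 | 0.64 | 0.70 |

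If the gap or the correlation has the opposite sign, each value becomes 1 minus the one shown.

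**Step 2: precision for comparison.** The null standard error of an AUC at 15 v 15 is √[(15 + 15 + 1)/(12 × 15 × 15)] = √(31/2700) = 0.107. The null 95% range is 0.5 ± 1.96 × 0.107, about 0.29 to 0.71.

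**Step 3: effect on a test.** A simple mean comparison stands in for the planned analyses (4,000 simulated trials per row, two-sided 0.05, no dizziness effect, linear age effect).

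| r | D | Rejection rate, unadjusted | Rejection rate, age-adjusted | Adjusted / unadjusted SE |
|---|---|---|---|---|
| 0.3 | 0 | 0.047 | 0.045 | 0.97 |
| 0.3 | 0.5 | 0.069 | 0.048 | 1.01 |
| 0.3 | 1.0 | 0.130 | 0.050 | 1.10 |
| 0.3 | 1.5 | 0.217 | 0.051 | 1.23 |
| 0.5 | 0 | 0.051 | 0.052 | 0.88 |
| 0.5 | 0.5 | 0.105 | 0.045 | 0.92 |
| 0.5 | 1.0 | 0.262 | 0.053 | 1.00 |
| 0.5 | 1.5 | 0.503 | 0.052 | 1.13 |

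The adjusting model matches the simulated age effect by construction. Its good performance is therefore a best case.

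**Step 4: chance imbalance.** Even if both groups came from one source, the standardized age gap would have standard error √(2/15) = 0.365. Then P(|gap| > 0.5) = 0.17 and P(|gap| > 0.25) = 0.49. Chance gaps average out over repeated trials, as the D = 0 rows show, but they can still mislead in a single sample.

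**The case against.** The strongest reply has four parts.

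1. **The age gap is not established.** A reader might infer that campus emails will yield a young healthy group and clinics an older dizzy one. The documents do not support this. Campus emails reach faculty and staff as well as students. Emails and advertisements are open to either group, and the Recruitment background puts motion-sickness symptoms at about a third of adults, so these routes can also supply symptomatic participants. This part stands: the gap is a possibility.
2. **The protocol does not call ageing a cause.** A reader might take the Background that way. It says the condition occurs across populations, including people with age-related changes; the cause it proposes is visual dependence. It would also be wrong to say that nothing makes the groups alike, because the shared eligibility criteria do part of that work. What is missing is balance on age and sex inside those limits.
3. **The size is assumed and imprecision is comparable.** At r = 0.4 and D = 1, the AUC of 0.61 is about one null standard error from 0.5, and 0.70 is still inside the null 95% range. This stands as a limit on size. It does not remove a systematic shift, which more participants recruited the same way would not cure.
4. **The study is preliminary.** Its inferential analyses are labelled hypothesis generating. That lowers the stakes, but Aim 1 exists to estimate accuracy, and a biased estimate could misdirect the next study.

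Elaborate remedies would also fit badly. Three age bands by two sexes make six cells for 15 people, and an age regression fitted in 15 healthy participants extrapolates where ages do not overlap.

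**Conclusion.** The point holds in a limited form. Aims 1 and 2 are unadjusted comparisons of non-randomized groups over a 61-year age range, in a protocol that links age to both the condition and the functions being tested. The AUC and the IP-curve difference may therefore partly reflect age.

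The size depends on two quantities the documents do not give. Over the assumed ranges, the AUC from age alone runs from no distortion (0.50) to 0.70. No size has been worked out for sex. The stronger conclusion, that the tests would be measuring age and not dizziness, does not follow: neither the existence nor the direction of an age gap is known.

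Aim 3's pre-post comparisons are within person and are not confounded by baseline age in the same way. This is a low-cost improvement of moderate priority and does not invalidate the design.

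**What to change.** **At enrolment, if still open.** Use the age and gender collected at telephone screening (Participant Screening) to keep the healthy group roughly similar to the symptomatic group in age, for example over two or three broad bands, and in overall sex ratio. Exact cell-by-cell matching is not needed. Some recruitment text is already in the past tense; if enrolment has closed, only the analysis changes apply.

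**In the analysis plan.** Report age and sex by group, and pre-specify one age-adjusted sensitivity analysis per aim:

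- **Aim 1:** an age-adjusted AUC for each verticality test from a pooled model of score on group and age. Under normality this is Φ(b/(s√2)), where b is the group coefficient and s the residual SD.
- **Aim 2:** a permutation test of the Euclidean distance between group IP curves, with group labels permuted only within age bands. This keeps the planned whole-curve comparison.

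Present adjusted and unadjusted results together, and limit any statement about diagnostic value to what the age-adjusted result supports.

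**Cost.** Some healthy places may fill a little more slowly, and each aim gains one analysis. The adjusted estimate may be less precise if ages overlap poorly: in the simulation its standard error was 0.88 to 1.23 times the unadjusted one. With 30 people, adjustment beyond one or two covariates would be weak, so balance at enrolment is preferable where possible.
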